### 6.3.2 Extent of Exposure to Study Medication

The total dose received, number of treatment cycles received, and dose intensity will be derived using data from the TAS-114 and S-1 Administration form, and Study Drug Accountability form.

The **total dose received** for each study drug is the sum of dose received at each cycle, and the number of cycle received is the number of cycles with at least one dose taken during a cycle.

The **treatment duration** for each study drug (in weeks) is calculated from the date of first dose to the date of last dose + 7 or the start of new anti-cancer treatment, whichever is earlier, and then divided by 7.

**Dose intensity** is defined as the total dose actually received divided by the planned dose (i.e., total dose that would be given if no doses were missed and/or no dose reductions were made for the duration of time the patient received any component of study treatment) multiplied by 100%.

The planned dose for each drug at each cycle is as follows:

- TAS-114: 400 mg x 2 (BID) x 14 Days
- S-1: 30 mg/m^2 x BSA x 2 (BID) x 14 Days  
where BSA (m^2) = ([Body Weight (kg)]0.425 x [Height (cm)]0.725) x 0.007184.

The total planned dose is the sum of planned doses over all cycles.

The number of dose reductions, dose modifications, dose interruptions, and cycle delays will also be calculated.

### 6.3.3 Adverse Events

Adverse events will be coded using the Medical Dictionary for Regulatory Activities (MedDRA version 19.0) and the severity of the toxicities will be graded according to the NCI CTCAE (Version 4.03).

Only treatment emergent adverse events will be included in summary tabulations. Treatment-emergent adverse events will be defined as adverse events with onset dates on or after the first dose of study medication and within 30 days after the last dose of study medication. Adverse events will be summarized by system organ class (SOC) and preferred term (PT), and worst severity grade.

#### Adverse Events Counting Rules

1. A patient with more than one different adverse event in a particular system organ class (SOC) will be counted only once in the total of patients experiencing adverse events in that particular SOC.

2. A patient having experienced the same event (AE preferred term) more than once during the study will be counted only once in the number of patients with that event.
3. If an event changes in intensity or in seriousness during the study, it will be counted only once with the worst grade and seriousness respectively.
4. If the causal relationship to the study drug is assessed differently, it will be counted only once by considering the “Worst” documented degree of relationship.

#### Missing Grade

An AE with missing severity grade will not be imputed but will be considered as ‘>=3’ in the table presenting Grade 3 and above.

#### Missing Relationship to Study Drug

An AE with a missing relationship to study drug will be deemed as reasonably possible. Imputed values will not be listed in data listings.

#### Adverse Events with Incomplete Dates

The following algorithm should be used to estimate adverse event start dates for which only partial information is known:

- Missing day and month
  - If the year is same as the year of first day on drug, then the day and month of the start date of drug will be assigned to the missing fields.
  - If the year is prior to the year of first day on drug, then December 31 will be assigned to the missing fields.
  - If the year is after the year of first day on drug, then January 1 will be assigned to the missing fields.
- Missing month only
  - Treat day as missing and replace both month and day according to the above procedure.
- Missing day only
  - If the month and year are same as the year and month of first day on drug, then the start date of drug will be assigned to the missing day.
  - If the month and year are before the year and month of first day on drug, then the last day of the month will be assigned to the missing day.
  - If the month and year are after the year and month of first day on drug, then the first day of the month will be assigned to the missing day.

If the AE stop date is complete and the imputed start date as above is after the stop date, the start date will be imputed using the stop date.

Adverse events with partially missing stop dates will be imputed a stop date as follows:

- *year is missing* - date left missing.

- *month is missing* - impute 'December'.
- *day is missing* - impute 'last day of that month'.

#### 6.3.4 Deaths

All deaths will be captured on the Death/Autopsy Form.

#### 6.3.5 Laboratory Data

Laboratory assessments include:

- Hematology: red blood cell (RBC) count, hemoglobin, hematocrit, platelets, white blood cell (WBC) count with differential, neutrophils (both segmented and band neutrophils), lymphocytes, monocytes, eosinophils, basophils.
- Serum chemistry: aspartate aminotransferase (AST), alanine aminotransferase (ALT), alkaline phosphatase (ALK), albumin, total bilirubin (direct bilirubin, indirect bilirubin), creatinine, sodium, potassium, calcium, chloride, blood urea nitrogen (BUN) or urea, phosphorus, bicarbonate, glucose, creatine kinase (CK)/creatine phosphokinase [CPK] (creatine kinase MB, creatine kinase MM) .
- Coagulation: international normalized ratio (INR), activated partial thromboplastin time (aPTT)
- Urinalysis: urinary protein (qualitative), urinary glucose (qualitative), and urine specific gravity density.

All laboratory data will be stored in the database with the units in which they are originally reported. Laboratory data in summary tables and subject data listings will be presented in the International System of Units (SI units; *Système International d'Unités*). Laboratory data not reported in SI units will be converted to SI units before further processing or data analysis.

Baseline value is the subject's last observation prior to the initiation of study drug (including Cycle 1 Day 1).

Laboratory tests will be graded using NCI-CTCAE v4.03 toxicity grading (see [Appendix 1](#)).

**Time to maximum/worst grade 3 or 4 value** (in days) is defined as the time from the date of first study treatment to the earliest date of maximum or minimum (nadir) laboratory parameter value with Grade 3 or above: (date of maximum/worst grade 3 or above – date of first study treatment + 1). If toxicity grade is defined for abnormal high/increase in NCI-CTCAE grading criteria, maximum is used. Otherwise, minimum (nadir) is used.

If there is no grade 3 or 4 laboratory value, the time to worst grade 3 or 4 value analysis will be censored at their last available laboratory assessment before the initiation of any new anti-cancer treatment, if applicable.

**Time to resolution** (in days) is defined as the time from the date of the worst grade 3 or 4 value to the earliest date of the laboratory parameter value return to baseline grade or below with an improvement of at

least one grade for the same type of abnormality (high/low): (date of return to baseline grade or below – date of worst grade 3 or above +1).

In case the laboratory value does not return to baseline grade or below, the time to resolution analysis will be censored at their last available laboratory assessment before the initiation of any new anti-cancer treatment, if applicable.

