8.1.1. Study Duration

Patients will receive the study drug according to the proposed treatment schedule until progressive disease (PD), occurrence of intolerable side effects, removal by the Investigator, or withdrawal of consent. A patient is considered discontinued from study treatment when either TAS-114/S-1 or S-1 alone is discontinued.

For the purpose of the final analyses, the study will be considered completed when all patients have discontinued from treatment or a minimum of 12 months from the date of the first day of treatment with TAS-114/S-1 or S-1 of the last patient enrolled or until the target number of

events (deaths, n=80) is reached, whichever occurs last. This analysis may still be done even if there are patients still on treatment.

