14.1.3. Safety

The safety evaluations will focus on the AEs and laboratory assessments. All patients included in the safety population will be evaluated in the safety analysis.

Adverse events will be coded according to the Medical Dictionary for Regulatory Activities (MedDRA) terminology and the severity of the toxicities will be graded according to the NCI CTCAE (Version 4.03) where applicable. Concomitant medications will be coded according to World Health Organization (WHO) Drug Dictionary for Concomitant Medication.

All AEs will be summarized (incidence) and listed by the system organ class, preferred term, toxicity/severity grade, and causal relationship to TAS-114/S-1 or S-1 control. In addition, separate summaries of SAEs and grade 3 or 4 AEs will be presented.

Hematological and chemistry laboratory parameters will be graded according to the NCI CTCAE (Version 4.03) where applicable. The worst severity grade, time to maximum grade 3 or 4 value, and time to resolution (return to baseline grade or below) will be summarized.

CCI

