### **7.1.5 Laboratory Data**

Hematology, serum chemistry, and coagulation results will be summarized by toxicity grade (using NCI-CTCAE v4.03 toxicity grading – see [Appendix 1](#) at baseline and post-baseline measurements that worsened by at least one grade. Local laboratory ranges will be used for grading. In the event a range is not available a standard set of lab ranges as detailed in [Appendix 3](#) will be utilized and flagged in the database.

The worst change from baseline in toxicity grade for selected laboratory parameters will also be presented in shift tables: in each treatment arm, the patient's baseline grade will be cross-tabulated by the patient's maximum post-baseline grade during the treatment.

Time to maximum/worst grade 3 or 4 value and time to resolution will be summarized for all quantitative laboratory parameters if toxicity grade is defined in NCI-CTCAE v4.03. The Hematology parameters will include Hemoglobin, Hematocrit, RBC, WBC, ANC, Thrombocytopenia, and Platelets, and the Chemistry

parameters will include AST, ALT, Total Bilirubin, and Alkaline Phosphatase. Count of the events and the censored, minimum and maximum of the event time will be presented by treatment group. Meanwhile, median time to worst grade 3 or 4 value and time to resolution for each group being compared will be estimated using the Kaplan-Meier method, along with the corresponding 95% CI.

The qualitative urinalysis results will be summarized by visit and treatment groups. A shift table for qualitative urinalysis results from baseline to worst past-baseline will also be presented.

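### Kaplan-Meier timing of the worst Grade 3/4 laboratory value uses a date known only in hindsight: it understates early toxicity in both arms and can make equal toxicity look later in the longer-treated arm

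*SAP*

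**What the plan says.** Protocol 14.1.3 asks that "time to maximum grade 3 or 4 value, and time to resolution (return to baseline grade or below) will be summarized". SAP 6.3.5 makes this concrete: the clock runs from first study treatment "to the earliest date of maximum or minimum (nadir) laboratory parameter value with Grade 3 or above". The word earliest only settles ties between equal extremes; no cycle or fixed window is set. For a patient with no such value, "the time to worst grade 3 or 4 value analysis will be censored at their last available laboratory assessment" before any new anti-cancer treatment. Time to resolution "is defined as the time from the date of the worst grade 3 or 4 value to the earliest date" of return to the baseline grade or below, so it starts at the same worst-value date.

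SAP 7.1.5 then states that "median time to worst grade 3 or 4 value and time to resolution for each group being compared will be estimated" by Kaplan-Meier with 95% CIs. No test is attached.

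The readable text has no time to first Grade 3/4 value, no landmark and no window equal for both arms. Shift tables of maximum post-baseline grade (SAP 7.1.5) and adverse event incidence by grade (SAP 7.1.3) are planned, but neither describes timing.

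**The concern.** Kaplan-Meier needs an event that can be recognised on the day it happens. Whether a given value is the patient's worst cannot be known until all later values are in. A patient with a Grade 4 count in Cycle 1 and a slightly lower one in Cycle 3 is carried as event-free for the two cycles between.

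Two consequences follow. First, the early part of the curve is too low in both arms. Second, the date depends on how long the patient is sampled. Treatment runs to progression, intolerable toxicity, removal or withdrawal (Protocol 8.1.1), so sampling time can differ by arm. The medians are tabulated side by side, and safety and tolerability is a secondary objective. A reader could take a longer median as later onset of toxicity when it reflects only longer observation.

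**Working it through.** **Inputs from the documents.** Event and censoring rules: SAP 6.3.5. Cycle length of 21 days: Protocol 9.1.1. Laboratory days: Cycle 1 Days 8 and 15, then Days 1 and 15, with Day 15 not required after Cycle 4 unless clinically indicated (Protocol 11.7.1). The plan gives no figure for this endpoint. The design PFS medians are 2.2 and 4.2 months (Protocol 14.2). They reproduce the plan's own figures: 2.2/4.2 = 0.524, and 4 × (1.645 + 0.842)² / (ln 0.524)² = 24.74/0.418 = 59.2, rounded up to 60 events.

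**Assumed, because the documents are silent.** Treatment duration is exponential with those two medians. Toxicity rate, recurrence and the effect of dose reduction are varied, and toxicity at the starting dose is the same in both arms.

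**Step 1: direction.** Let F be the first Grade 3+ date and W the date of the worst value after n samples. If F exists, W ≥ F. One more sample leaves W unchanged or moves it to the new date. If a patient's cycle nadirs are exchangeable and all are seen, the worst of n falls on average at cycle (n + 1)/2. The two medians are 2.2 × 30.4375 = 67 days (67/21 = 3.2, so 4 cycles) and 4.2 × 30.4375 = 128 days (128/21 = 6.1, so 7 cycles). The average position is then (4 + 1)/2 = 2.5 against (7 + 1)/2 = 4.0, with no difference in toxicity.

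**Step 2: neutrophil model.** 100,000 patients per arm; nadir on Day 15, lognormal with median 1600/mm³, between- and within-patient log SD 0.5 each; Grade 3+ taken as below 1000/mm³; no dose reduction. Chance per cycle = Φ(ln(1000/1600)/√(0.25 + 0.25)) = Φ(−0.470/0.707) = 25%.

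| Nadirs seen | Measure | 2.2-month arm | 4.2-month arm |
|---|---|---|---|
| Every cycle | Median to worst | 99 days | 141 days |
| Every cycle | Day 36, worst | about 27% | about 21% |
| Cycles 1–4 only | Median to worst | 78 days | 78 days |
| Cycles 1–4 only | Day 36, worst | about 31% | about 29% |
| Either | Median to first | 78 days | 78 days |
| Either | Day 36, first | about 38% | about 38% |

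The gap is 141 − 99 = 42 days at one extreme and 0 at the other. Event dates lie on a 21-day grid, so equal medians can hide a small shift. With Cycles 1–4 only, the mean time to worst among patients with an event is about 39 vs 42 days.

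**Step 3: second model.** 15,000 patients per arm on the planned laboratory days, with equal chance p of a Grade 3+ value per visit, between-patient SD 0 or 1, and a dose-reduction effect of 0, 0.5 or 1 SD per level (18 scenarios). Shorter- vs longer-treated arm:

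| p, SD, dose effect | Median to worst | Median to first | Day 63, worst |
|---|---|---|---|
| 0.10, 0, 0 | 78 vs 92 | 64 vs 64 | 39.0% vs 34.9% |
| 0.20, 0, 0 | 57 vs 64 | 36 vs 36 | 55.8% vs 47.2% |
| 0.20, 1, 0 | 78 vs 113 | 57 vs 57 | 41.5% vs 34.1% |
| 0.20, 1, 1 | 57 vs 64 | 57 vs 57 | 50.4% vs 49.2% |
| 0.20, 0, 1 | 36 vs 36 | 36 vs 36 | 70.4% vs 67.7% |

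Over all 18 scenarios the Day 63 gap for time to worst runs from −0.3 to +8.6 points. For time to first the arms differ by at most 1.3 points. In a control run with equal durations, Day 63 incidence was 21.8% vs 21.7% (worst) and 31.7% vs 31.2% (first): the arm gap vanishes but the understatement stays.

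**Caution on late medians.** With p = 0.10, SD 1 and a dose effect of 1, the medians are 232 vs 274 days (worst) and 274 vs 295 days (first). The time-to-first medians differ by 21 days although the rates are equal, so medians this late are unreliable. The worst-value curve has also crossed the first-value curve by then. The understatement is a statement about early incidence.

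**The case against.** The strongest reply is that the schedule and dosing rules limit the drift. After Cycle 4 the only routine sample is the pre-dose Day 1 sample, and a cycle may not start until neutrophils are at least 1500/mm³ (Protocol 9.1.2.4). A late, lower nadir may then need an unscheduled test. Related non-hematologic Grade 3+ toxicity generally leads to a dose reduction (Protocol 9.1.2.2.1), which makes a second, worse value less likely. This stands: it is why the gap can be 0, and why 42 days should not be read as an estimate. It does not remove the mechanism. Uncomplicated neutropenia or thrombocytopenia up to Grade 3 requires no reduction, and uncomplicated Grade 4 with a delay of one week or less restarts at the same dose (Protocol 9.1.2.2.2), so repeat nadirs at full dose are possible within the first four cycles.

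A reader might infer that the metric flatters TAS-114/S-1. The documents do not support that. They give design PFS medians, not treatment durations; treatment also ends for toxicity; and stopping either drug counts as discontinuation in the combination arm (Protocol 8.3). Without longer treatment on the combination, the bias between arms vanishes or reverses.

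A reader might extend the point to liver tests, but neither model represents them and the reduction rule works against it. Nor is there a protocol–SAP conflict, since the SAP follows the protocol. Time from the worst value to resolution is a labelled, legitimate quantity; it simply leaves out Grade 3/4 time before the worst value.

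Finally, these medians are descriptive, and toxicity burden is tabulated elsewhere. That limits the consequence to this one summary.

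**Conclusion.** The point holds as a modest fault in a descriptive safety summary. The early curve is too low in both arms: at Day 36 in the neutrophil model with nadirs seen only in Cycles 1–4, by about 38 − 31 = 7 points in one arm and 38 − 29 = 9 in the other. The apparent delay between arms depends on which arm is treated longer. If durations follow the design PFS medians, it runs from 0 days (nadirs seen only in Cycles 1–4, or a strong dose-reduction effect) to about 42 days (nadir seen in every cycle, no dose reduction). Rates, recurrence, dose-reduction effect and durations are all assumptions. The concern is strongest for neutrophils and platelets and is not shown for liver parameters. The PFS analysis, its alpha and the sample size are untouched.

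**What to change.** In SAP 6.3.5 and 7.1.5, add time from first dose to the first Grade 3 or higher value, with the censoring rule already stated, and make it the Kaplan-Meier comparison by arm. Keep the protocol-named time to worst value as a descriptive supplement, preferably within a window equal for both arms, such as Cycle 1. State beside time to resolution that it runs from the worst value and so excludes earlier Grade 3/4 time.

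The cost is one extra derivation and one extra table. No new data are needed. Because the protocol-named summary stays, no protocol amendment is needed; SAP 8 already allows documented revisions before database lock.

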6.2.1.5. Toxicology

No effect of TAS-114 on the central nervous system or respiratory system was observed after single-dose oral administration at doses up to 1000 mg/kg in rats. In studies of the cardiovascular system, TAS-114 suppressed the human ether-a-go-go related gene current at doses of 10 $\mu\text{mol/L}$ or higher in vitro (a concentration about 6 times higher than the mean maximum observed plasma concentration (C_{max}) value in human subjects administered 300 mg/body TAS-114); however, in conscious dogs, no effect was observed after single-dose oral administration at doses up to 500 mg/kg.

Multiple dose toxicity was examined in rats and dogs including 4-week oral toxicity studies.^{12,13,14} The observed significant toxicities included: a prolongation of prothrombin time or activated partial thromboplastin time, slight vacuolation in the hepatocytes, decreased body weights, decreases in white blood cell (WBC) and erythrocyte counts, and atrophic changes in the lymphatic and hematopoietic tissues. No observed adverse effect levels were determined to be 200 mg/kg/day in rats and 10 mg/kg/day in dogs based on the 4-week repeated oral dose toxicity studies.

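### For a laboratory parameter that CTCAE grades both high and low, the SAP's worst-value rule never uses the nadir, so Grade 3/4 low values can be lost or misdated in two timing summaries

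*SAP*

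**What the plan says.** Protocol 14.1.3 promises three laboratory summaries: worst severity grade, time to maximum Grade 3 or 4 value, and time to resolution. It sets no limit by direction of abnormality.

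SAP 6.3.5 turns the last two into derivations:

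- The event in the first is "the earliest date of maximum or minimum (nadir) laboratory parameter value with Grade 3 or above".
- The choice between the two extremes is: "If toxicity grade is defined for abnormal high/increase in NCI-CTCAE grading criteria, maximum is used. Otherwise, minimum (nadir) is used".
- Censoring: "If there is no grade 3 or 4 laboratory value, the time to worst grade 3 or 4 value analysis will be censored" at the last available assessment before any new anti-cancer treatment.
- Time to resolution is "defined as the time from the date of the worst grade 3 or 4 value" until the parameter is back at baseline grade or below, with an improvement of at "least one grade for the same type of abnormality (high/low").

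SAP 7.1.5 says that both times "will be summarized for all quantitative laboratory parameters if toxicity grade is defined in NCI-CTCAE v4.03". It then names parameters: "The Hematology parameters will include Hemoglobin, Hematocrit, RBC, WBC, ANC, Thrombocytopenia, and Platelets", and for chemistry AST, ALT, total bilirubin and alkaline phosphatase.

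**The concern.** The selection rule is an if/otherwise rule applied to a parameter, and the existence of a high-side grade settles the direction for every patient. If a parameter also has a low-side grade, the second branch is never reached and the smallest value is not examined.

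The resolution definition, by contrast, refers to the direction of the abnormality, so the SAP has both kinds in view. The rule that supplies its start date does not follow suit.

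At stake is whether two of the three laboratory outputs promised in Protocol 14.1.3 report low-side Grade 3/4 values correctly. If they do not, these tables can also disagree with the worst-grade and shift tables for the same parameter, with nothing in the SAP to explain the difference.

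**Working it through.** The plan gives no figure to reproduce; this is a check of a derivation rule.

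**Step 1: the branches.** For a given parameter:

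| CTCAE grades defined | Branch taken | Extreme used | Low side captured? |
|---|---|---|---|
| High only | first | maximum | not applicable |
| Low only | otherwise | nadir | yes |
| High and low | first | maximum | no |

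Only the third row fails. No other section of the SAP derives the low direction separately.

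**Step 2: two ways to program the sentence.** Reading A takes the maximum over all of the patient's values and asks whether it is Grade 3 or above. Reading B first keeps the values of Grade 3 or above, then takes the maximum of those.

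**Step 3: hypothetical patients, not trial data.** Take one parameter graded both ways on an arbitrary scale: Grade 3 at -3 or +3, Grade 4 at -4 or +4, measured on days 1, 8, 15, 22 and 29, with first treatment on day 1. The last column applies the rule separately by direction.

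| Patient | Values on days 1, 8, 15, 22, 29 | Reading A | Reading B | By direction |
|---|---|---|---|---|
| Low only | 0, -3, -4, -1, 0 | no event | day 8 | low: day 15 |
| High only | 0, 3, 4, 1, 0 | day 15 | day 15 | high: day 15 |
| Both | 0, -4, 0, 3, 0 | day 22 | day 22 | low: day 8; high: day 22 |
| Neither | 0, -1, 1, 0, 0 | no event | no event | no event |

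For the low-only patient, reading A finds a maximum of 0 and therefore no event. Reading B finds -3 and -4, and the larger is -3, so it picks the Grade 3 value on day 8 and passes over the Grade 4 value on day 15. (With a single low Grade 3/4 value, reading B would give the right date.) For the patient with both, each reading returns the high Grade 3 on day 22 and loses the low Grade 4 on day 8. Neither reading selects on the nadir.

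**Step 4: time to resolution.** The SAP formula is resolution date minus date of worst value, plus 1.

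- Low only, by direction: 29 - 15 + 1 = 15 days. Reading B: 29 - 8 + 1 = 22 days. Reading A: there is no start date, so nothing is derived.
- Both, by direction: low 15 - 8 + 1 = 8 days and high 29 - 22 + 1 = 8 days. Readings A and B give the high episode only.

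**Step 5: censoring.** Under reading A the low-only patient has no event. The censoring sentence applies only where no Grade 3/4 value exists, and this patient has two. The SAP therefore gives the patient neither an event nor a censoring date.

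**The case against.** The strongest reply is that a sensible programmer would apply the rule to each CTCAE term, not to each parameter: maximum for terms graded high, nadir for terms graded low. Two features of the SAP lean that way. The resolution definition speaks of the type of abnormality, and the 7.1.5 list contains both thrombocytopenia and platelets, so it mixes a toxicity term with a parameter. That reading is possible and would give the right answer. But 6.3.5 defines the event on the parameter value and nowhere says that the rule runs per term; the mixed list shows only that the unit is unsettled.

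The second reply is about reach, and it stands. Nothing in the available documents shows which parameters are graded both ways, and the reference to high and low in the resolution definition could be generic wording covering some high-graded and some low-graded tests.

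Three stronger inferences should be resisted:

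- *That Grade 3/4 low values are hidden from the report.* They are not. The grade summaries and shift tables in SAP 7.1.5 do not use this rule, and adverse events are tabulated by grade in SAP 7.1.3.
- *That low electrolytes are lost.* The chemistry tests named in SAP 7.1.5 include no electrolyte. The general clause before them is wider, so the scope is unclear, but no such loss is shown.
- *That the rule misses the direction in which TAS-114 is known to be toxic.* Protocol 6.2.1.5 does report "decreases in white blood cell (WBC) and erythrocyte counts", but from rat and dog studies, and the same list includes prolonged clotting times, which are high-side findings.

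**Conclusion.** The point holds as a conditional defect. For any analysed parameter that CTCAE v4.03 grades in both directions, following SAP 6.3.5 as written means the nadir is never used. Low-only patients are left without a status or may be misdated, patients with both kinds lose the low event, and time to resolution inherits either fault.

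Its size cannot be given. It rests on the grading table in SAP Appendix 1, which is not reproduced, and on whether the list in SAP 7.1.5 is complete or only illustrative. If no analysed parameter is graded both ways, the effect is nil. A reader might want to put a number of censored patients per arm on it; the documents give no low-side Grade 3/4 rate, and the censoring sentence does not cover these patients anyway, so no such count is supported.

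The consequence is confined to two descriptive safety outputs. The rule is the same in both arms, and the PFS test and sample size are untouched. It still deserves correction, because it is a stated rule that gives a wrong result when followed, not merely a missing detail.

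**What to change.** In SAP 6.3.5, replace the selection sentence with a rule to this effect: derive time to worst Grade 3/4 value and time to resolution separately for each CTCAE term and direction, using the nadir for terms graded on low values and the maximum for terms graded on high values; a parameter graded both ways contributes two analyses. Start each time to resolution from the worst value of the same term. Define censoring in the same way, so that a patient is censored for a term when there is no Grade 3/4 value in that direction.

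The cost is one revised sentence and a few more table rows, with no new data. SAP section 8 already provides for a documented revision before database lock. If Appendix 1 turns out to hold no parameter graded both ways, the new wording changes no result.
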